9.8 Recurrent Atrial Fibrillation

Endpoint definition: This particular outcome will be analyzed with different endpoint definitions in order to provide an overall perspective of the extent of the AF burden experienced by the study subjects. The first analysis will consider the first episode of recurrent AF as the endpoint, defined as an episode ≥ 30 seconds following the end of the 90-day blanking period, where the 90-day blanking period begins at the time of receiving the randomly assigned treatment (either ablation or drug therapy). The endpoint will be defined as the time until the first recurrence of AF according to this definition. Similar analyses will be performed where the endpoint is defined as: (a) an episode of *symptomatic* recurrent AF, (b) an episode of atrial fibrillation or atrial flutter or atrial tachycardia, and (c) an episode of *symptomatic* atrial fibrillation, atrial flutter, or atrial tachycardia.

Analysis Population: Because recurrent atrial fibrillation is defined with respect to the end of the blanking period, which begins after receipt of the assigned treatment, all analyses for recurrent atrial fibrillation will include only patients who have received their randomly assigned treatment and live to the end of the blanking period.

In addition, separate analyses will be performed according to the method used for monitoring AF recurrence. As indicated in Section 6 (Data Sources), rhythm data for many of the patients enrolled in CABANA (approximately 2/3 of the randomized patients) are collected using the “CABANA Box,” a robust rhythm monitoring system provided by Medicomp. The rhythm monitoring data are sent from Medicomp to the Duke Clinical Research Institute (DCRI), where a set of programmed rules are run to determine which rhythms should be submitted to the ECG core lab for review and adjudication. Following core lab review, the adjudicated results are electronically transmitted back to the DCRI. Sites that are not using the “CABANA Box” (generally these are international sites where use of the CABANA Box was not approved) submit rhythm data through a secure portal using the CABANA website, which is then processed and submitted to the core lab for adjudication. Because the CABANA Box data are more comprehensive and more routinely and rigorously collected, separate analyses of recurrent atrial arrhythmias will be performed using (a) patients whose rhythms were monitored using the CABANA Box, (b) all remaining patients (i.e., non-CABANA Box patients), and (c) the pooled group of all patients (with use of CABANA Box as a covariate if justified). In the case of

patients who initially used the CABANA Box and later ceased to provide information via CABANA Box, the analysis will censor that data at the time of last CABANA Box recording. The primary analysis of this endpoint will be the analysis of patients with CABANA Box data because of the more comprehensive collection of that rhythm monitoring information. Analysis which includes non-CABANA Box patients (“b” and “c” above) will be considered supplementary analysis.

Statistical Analysis: First, descriptive summaries of baseline characteristics of subjects receiving their assigned treatment and living to the end of the blanking period in both treatment arms will be presented to determine how comparable the patients in the two arms are for this analysis. Continuous variables will be presented in terms of percentiles (median, 25th and 75th percentiles), while discrete variables will be summarized in terms of frequencies and percentages.

The treatment arms will be compared using statistical methods described in the sections above for other secondary endpoints, including the competing risk method of Fine and Gray⁴, as well as use of the log-rank test, hazard ratio and 95% confidence interval generated using the Cox model, and Kaplan-Meier cumulative event rate calculations. In this case, all-cause mortality will be a competing risk and zero-time (i.e., when the clock starts) for this analysis will be the end of the 90-day blanking period. Analyses will be repeated with adjustment for the baseline covariates described in section 8.1.

Of key interest will be whether the effect of ablation on recurrent atrial arrhythmias is similar or different according to the type of AF the patients experienced prior to enrolling in the trial (i.e., whether the effect varies according to whether patients’ baseline AF was paroxysmal, persistent or long-standing persistent). This analysis will utilize the Cox model to test for an interaction between the randomized treatment strategy and the baseline type of AF classified as (a) paroxysmal or (b) persistent or longstanding persistent. In addition to the interaction test, the effect of the treatment strategy characterized by a hazard ratio and 95% confidence interval and Kaplan-Meier event rate calculations will be calculated and displayed for the subgroups of patients whose baseline AF history was (a) paroxysmal and (b) persistent or longstanding persistent. Similar comparative analyses will be performed in subgroups defined by age (<65, 65-74, and ≥75) and by CHA₂DS₂-VASc Score (0 or 1 vs >1).

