4.4 Post Randomization Procedures

For morbidity and mortality end points, intention-to-treat analysis will begin at randomization. All therapies will be established and optimized in a 3-month treatment initiation period, during which patients may receive alternative drugs or undergo repeat ablation if AF recurs. The duration of this “blinking period” is derived from standard clinical practice and the AF Ablation Consensus Document [50, 51]. Thereafter, therapy will be administered and patients followed for an average of approximately 5 years. Efficacy, (i.e. absence of AF recurrence) will be established by long-term follow-up beginning after the 3-month therapy initiation phase. Any AF occurring after the 3-month blinking period will be considered a treatment failure for the AF recurrence secondary endpoint. Patients will be followed at 6 and 12-month intervals from randomization throughout the trial.

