6.2 Secondary Endpoints & Safety Endpoints

Secondary endpoint events, including total mortality and a composite of total mortality or cardiovascular hospitalization will be confirmed.

While hospitalization for any atrial fibrillation, atrial flutter or atrial tachycardia in both treatment arms will be carefully tracked and compared, it will be considered as an "AF recurrence" and counted against efficacy, not safety. Therefore, *AF recurrence and/or worsening of AF need not be reported as an adverse event.*

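### SAP 9.8 does not count as recurrences the AF, flutter and atrial tachycardia admissions that Protocol 6.2 assigns to the AF recurrence endpoint

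*SAP*

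**What the plan says.** Protocol 6.2 states that "hospitalization for any atrial fibrillation, atrial flutter or atrial tachycardia in both treatment arms will be carefully tracked and compared". Such an admission is to be regarded as an AF recurrence "and counted against efficacy, not safety", and the section concludes that AF recurrence or worsening need not be reported as an adverse event. Section 7.0 repeats that exemption. Protocol 4.4 is neutral as to source: any AF after the 3-month blanking period "will be considered a treatment failure for the AF recurrence secondary endpoint". Protocol 6.1 says the specific reason for each hospitalization is determined by the site principal investigator and reported in the eCRF.

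SAP 9.8 takes as its first endpoint the first episode of recurrent AF, "defined as an episode ≥ 30 seconds following the end of the 90-day blanking period". Flutter and atrial tachycardia come in only under further definitions: (b), "an episode of atrial fibrillation or atrial flutter or atrial tachycardia", and (c), its symptomatic counterpart. The only inputs described, here and in SAP section 6, are Box recordings or rhythm data submitted through the web portal, adjudicated by the ECG core lab. Hospitalization is not mentioned. On the choice of data: "The primary analysis of this endpoint will be the analysis of patients with CABANA Box data". For patients who began with the Box and later ceased to provide data, "the analysis will censor that data at the time of last CABANA Box recording".

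**The concern.** The two documents define the event differently. The protocol moved AF, flutter and atrial tachycardia admissions out of safety reporting because they would be counted as recurrences. The SAP section that analyses recurrence has no place for them. It also has no AF-specific comparison of admissions between arms, although Protocol 6.2 promises one.

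Two things are at stake. First, recurrences serious enough to need admission can be missing from the endpoint meant to hold them. Second, a patient may stop using the Box because of rhythm, symptoms or a change of treatment. The trial is open-label, and Protocol 8.1 allows for 25-30% of drug-arm patients crossing over to ablation. Censoring at the last recording may therefore be related to the outcome, and differently so in the two arms.

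**Working it through.** There is no planned figure to reproduce: neither document gives an event rate, power, admission rate or Box discontinuation rate for this endpoint. The main check is to run the possible situations through both texts.

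| Post-blanking AF admission | Protocol 6.2 with 4.4 | SAP 9.8, Box analysis |
|---|---|---|
| On the Box; a recording has already qualified | event | event, same date as under the protocol |
| On the Box; a recording qualifies only later | event at admission | event at the later date |
| On the Box; no recording ever qualifies | event at admission | no event; time to last recording analysed as event-free |
| After the last Box recording | event at admission | censored earlier; later time leaves the risk set |

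An admission for flutter or atrial tachycardia alone is a recurrence under Protocol 6.2. Under the SAP's first definition it would not be an event even if recorded.

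**Patients affected.** SAP 9.8 puts Box patients at about two thirds of those randomized: 2/3 × 2,204 ≈ 1,469.

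**Scheduled recording (Protocol 4.4.3).** Year 1 has ten 24-hour and three 96-hour recordings: (10 × 24 + 3 × 96)/8,766 h = 528/8,766 = 6.0%. After blanking, months 4 to 12 have seven and two: (7 × 24 + 2 × 96)/(0.75 × 8,766) = 360/6,574.5 = 5.5%. Each later year has two and two: (2 × 24 + 2 × 96)/8,766 = 240/8,766 = 2.7%. Outside these hours, capture depends on the patient activating the device. Scheduled Box recording ends at month 60. These are hours observed, not the probability of missing a recurrence.

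**Illustration; every rate is assumed.** Let d be the yearly rate of a first Box-detected recurrence (0.40 drug, 0.20 ablation), and h the yearly rate of an AF, flutter or atrial tachycardia admission before any Box episode. With constant rates, during Box use HR(SAP) = d₁/d₀ = 0.20/0.40 = 0.50. Counting admissions, HR = (d₁ + h₁)/(d₀ + h₀):

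- h = 0.03 in both arms: 0.23/0.43 = 0.53
- h = 0.05 in both arms: 0.25/0.45 = 0.56
- h = 0.08 drug, 0.04 ablation: 0.24/0.48 = 0.50
- h = 0.04 drug, 0.08 ablation: 0.28/0.44 = 0.64

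**Share of patients.** A simulation over 4 years used the same rates, a Box-stopping rate c of 0.10 or 0.25 per year, and an admission rate that was unchanged or doubled after stopping. Per arm, about 2-11% of patients have an on-Box admission that never becomes a SAP event, about 2-7% have one counted only at a later Box episode, and about 1-14% have one after Box use ends.

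The 11% can be checked directly. With h = 0.08, d = 0.20, c = 0.10 and T = 4, the probability that an admission comes first and no Box episode follows before stopping or T is

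h × { [c/(d+c)] × [1 − e^(−(h+d+c)T)]/(h+d+c) + [d/(d+c)] × e^(−(d+c)T) × [1 − e^(−hT)]/h }

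= 0.08 × {0.3333 × 0.7813/0.38 + 0.6667 × 0.3012 × 0.2739/0.08} = 0.08 × (0.685 + 0.687) = 0.110.

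**The case against.** The strongest reply is that these admissions are not lost to the trial. SAP 9.2 counts every hospitalization the site designates as cardiovascular, apart from those to initiate therapy. It expressly includes drug-arm admissions for a therapy change or crossover and admissions for repeat ablation. SAP 9.9 analyses cardiovascular hospitalization alone, with recurrent events. That stands, and it rules out any reading that AF admissions vanish from the analysis. But those endpoints pool all cardiovascular causes, so they cannot show freedom from AF, which is where Protocol 6.2 placed these events.

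It can also be said that SAP 9.8 does not expressly exclude an episode documented during an admission. That is true; the point is an inference from the definition and the named data sources. It is a strong inference, because no route is described for a Box patient's hospital tracing, and someone programming from 9.8 would not count it.

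Third, the Box also takes patient-activated recordings, and sustained AF would probably appear at the next scheduled one. This reduces the loss during Box use by an unknown amount. It does nothing after Box use stops.

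Fourth, core-lab adjudicated data are less open to bias than site-reported reasons for admission in an open-label trial. That is a sound reason to keep the Box-only analysis, but not a reason to leave the protocol's rule unaddressed.

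**Conclusion.** The documents contradict each other on what counts as a recurrence, and following SAP 9.8 as written leaves out events that Protocol 6.2 assigns to this endpoint. The censoring at the last Box recording may be informative. Size and direction are unknown: the hazard ratios above rest wholly on assumed rates and range from no change to 0.64 against 0.50. This is a secondary endpoint, and the primary composite is untouched.

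A reader might infer more than the documents support:

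- That all missed admissions are analysed as event-free time. This is so only during continued Box use without a qualifying recording; after the last recording the patient has left the risk set.
- That crossing over to ablation triggers censoring. SAP 9.8 has no such rule; a patient who crosses over and keeps transmitting stays at risk.
- That freedom from AF is overstated in both arms. With informative censoring the direction depends on who stops the Box, which the documents do not show.
- That coverage of 6.0% or 2.7% of hours means most recurrences are missed. Coverage does not measure missed events.

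**What to change.** Reconcile SAP 9.8 with Protocol 6.2, stating whether a post-blanking admission for AF, flutter or atrial tachycardia is an event. Protocol 6.2 is silent on admissions during blanking; 4.4 suggests only later ones count, and this should be said.

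Keep the Box-only core-lab analysis and pre-specify an admission-inclusive analysis beside it. The first post-blanking admission for AF is an event on its date; for the broader definition (b), so is one for flutter or atrial tachycardia. Take the reason from the eCRF and leave out admissions to initiate therapy, as SAP 9.2 does. Do not assume that an admission meets the symptomatic definitions unless symptoms are recorded.

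Use one censoring rule for all patients in each version:

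- (i) count admissions up to the last Box recording, and censor everyone without an event there;
- (ii) count recordings and admissions up to last follow-up contact, and censor everyone without an event there.

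Adding post-Box admissions while still censoring the other patients at their last recording would bring in post-Box time only for patients with events, which is a new bias. Version (ii) has weaker detection after Box use stops, so it should be read with (i).

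Report time to last Box recording by arm. If Box-only remains the primary analysis, say that it departs from Protocol 6.2 and why.

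The cost is SAP wording and modest programming, since Protocol 6.1 already has the reason for admission collected. The downside is that this reason is site-reported in an open-label trial; the retained Box-only analysis addresses that.

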8.0 Statistical Considerations

8.1 Sample Size and Power Considerations

In initially planning the CABANA trial, several design factors and research objectives were considered in developing an appropriate sample size for the study. First, the number of patients was determined so there would be a sufficient number of endpoints to provide a high degree of confidence (power $\geq 90\%$) for testing the primary hypothesis. Second, important secondary endpoints were considered. Third, it was considered important for the overall sample to be large enough to permit a prudent examination of treatment effects in selected subgroups of patients where AF ablation might be particularly advantageous, or where the question of a treatment benefit from this invasive procedure is particularly relevant. Important pre-specified subgroups of interest in this study include those defined by age, gender, race, AF type (paroxysmal, persistent, or long-standing persistent), AF duration, heart failure class, presence/absence of underlying structural heart disease, presence/absence of hypertension, and ejection fraction. Finally, the sample size was determined to provide a reasonable level of confidence of detecting clinically important therapeutic effects even if current projections of event rates and treatment differences prove to be optimistic.

As described in Section 2.0, the study was originally designed with total mortality as the primary endpoint. However, in early 2013 a careful assessment of the progress of the trial was undertaken by the study leadership. Completely blinded to any treatment-specific outcome data, the two major issues addressed by the leadership group were (1) a lower than expected aggregated mortality rate, and (2) accrual of patients at a rate much slower than projected. Careful consideration of these issues led to a decision to (a) change the primary endpoint of the trial from total mortality to the key secondary endpoint consisting of the composite of death, disabling stroke, serious bleeding, or cardiac arrest, and (b) reduce the sample size to a number that was consistent with the new primary endpoint. The following paragraphs, which outlined the key considerations in determining the original sample size, are also relevant for the revised sample size.

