7.1. Demographic and Baseline Analyses

Descriptive summaries of the distribution of continuous baseline variables will be presented in terms of percentiles (median, 25th and 75th percentiles), while discrete variables will be summarized in terms of frequencies and percentages. Statistical comparisons of treatment groups with respect to baseline characteristics will be limited to selected variables and disease factors known to influence prognosis. These variables will include: age, sex, race, descriptors of comorbidity, heart failure class, type of AF (paroxysmal, persistent or permanent), years since onset of AF, days from most recent qualifying episode of atrial fibrillation to enrollment, presence/absence of structural heart disease, and CHA₂DS₂-VASc score. For comparisons of treatment groups with respect to continuous or ordinal baseline variables, the nonparametric Wilcoxon rank-sum test will be used. Group comparisons with respect to discrete baseline variables will use the Pearson's chi-square test or Fisher's exact test as appropriate.

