Differential treatment effects. If there is an overall difference in outcome between treatment groups, supplementary analyses will be performed to assess whether the therapeutic effect is consistent across all patients, or whether it varies according to specific patient characteristics. In particular, these analyses will focus on whether the relative therapeutic effect of ablation compared to drug therapy differs according to the following baseline variables:

- Age (<65 , 65 to 74, and ≥ 75 years)
- Sex (male vs. female)
- Race (white vs. racial minorities)
- AF type (paroxysmal vs. persistent, or long-standing persistent)
- Years since onset of AF (>1 vs ≤ 1)
- Days from most recent qualifying episode of atrial fibrillation to enrollment (>12 vs ≤ 12 days)
- NYHA Heart Failure Class at enrollment (no heart failure or Class I vs. \geq Class II)
- History of congestive heart failure (yes vs. no)
- Structural heart disease (present vs. absent)
- Hypertension (present vs. absent)
- Hypertension with LVH (present vs. absent)
- CHADS₂ (0 or 1 vs >1)
- CHA₂DS₂-VASc score (0 or 1 vs >1)
- Sleep Apnea (present vs. absent)
- Family history of atrial fibrillation (yes vs. no)
- Obesity (BMI ≥ 30 vs. < 30)
- Left ventricular ejection fraction (LVEF) (≤ 35 vs >35)
- North American vs. other international sites

These analyses will utilize the Cox model and will be accomplished by testing for interactions between the randomized treatment strategy and the specific baseline variables listed above. In addition to the formal assessment of treatment by covariate interactions, the effect of the treatment strategy characterized by a hazard ratio and 95% confidence interval will be calculated and displayed using a forest plot for the subgroups of subjects defined by the variables listed above. These descriptive hazard ratios will be carefully interpreted in conjunction with the formal interaction tests.

The effect of the treatment strategy may also be examined in other subgroups of clinical interest in addition to those listed above.

9. Analysis of Secondary Endpoints

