The time-dependent ablation variable to be included in the analysis will be created using 3 different methods: For method 1, the ablation variable starts as 0 (no ablation) for all patients. For patients who received ablation, the ablation variable is set to 1 at the time of ablation. In method 2, the ablation variable starts as 1 for all patients who were randomized to ablation and actually received ablation. For all other patients, the ablation variable is started as 0 and set to 1 at the time of ablation if they received ablation during the trial. Method 3 has the ablation variable started as 1 for patients who were randomized to ablation. For all other patients (i.e., randomized to drug), the ablation variable is started as 0 and set to 1 at time of ablation.

Among the 3 methods described above, method 2 will be considered the main statistical method in handling cross-overs via a time-dependent variable in Cox model. The other 2 methods are considered as sensitivity analyses.

Differential treatment effects for the primary endpoint and major secondary endpoints of interest using on-treatment analyses will also be conducted. Subgroups of interest will include those listed in section 8.1.

Because treatment assignment is no longer random, results can be biased by an association between the likelihood of treatment change and the risk of a clinical event (i.e., factors that make a patient more likely to cross over may also make them more likely to have an event). Thus, such analyses will be cautiously interpreted. Each of the analyses described in this section will be covariate adjusted using the covariates described in section 8.1 for the primary endpoint.

11. Per-Protocol Analysis

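### SAP 9.8 asks whether the ablation effect differs across three AF types but tests and displays only two, so it cannot show whether persistent and long-standing persistent AF respond differently.

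*SAP*

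**What the plan says.** SAP 9.8 puts the question in these words: "Of key interest will be whether the effect of ablation on recurrent atrial arrhythmias is similar or different according to the type of AF". It goes on to spell the types out, asking whether the effect varies according to whether "baseline AF was paroxysmal, persistent or long-standing persistent". The next sentence specifies a Cox interaction test between randomized strategy and "baseline type of AF classified as (a) paroxysmal or (b) persistent or longstanding persistent". The sentence after that limits the subgroup hazard ratios and Kaplan-Meier rates to patients whose "baseline AF history was (a) paroxysmal and (b) persistent or longstanding persistent".

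For the primary endpoint, the list under Differential treatment effects in SAP 8.1 gives "AF type (paroxysmal vs. persistent, or long-standing persistent". SAP 9.1 applies the 8.1 methods to all-cause mortality. SAP section 10 carries the list to the on-treatment analyses: "Subgroups of interest will include those listed in section 8.1".

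Protocol 8.1 names the prespecified subgroup as "AF type (paroxysmal, persistent, or long-standing persistent". Protocol 3.1 defines the three types separately for entry. Protocol 1.8 counts the influence of AF type on treatment outcome among the unsettled questions that the trial is to answer.

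Two places in the SAP do not merge the types. SAP 7.1 compares the arms at baseline on "type of AF (paroxysmal, persistent or permanent", which is three levels with a different name for the third. The adjustment covariate in SAP 8.1 is baseline AF type with no coding stated.

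**The concern.** A contrast of paroxysmal with everything else says nothing about differences inside the merged class. That class runs from an episode of at least 7 days to continuous AF of more than a year, which Protocol 3.1 treats as different conditions. The SAP poses a three-way question and, in the same paragraph, specifies an analysis that cannot answer it.

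Two errors of reading could follow. A benefit present only in persistent AF could be taken to cover long-standing persistent AF as well, because both would sit under one hazard ratio. Or a real effect in one of the two could look weaker than it is because it is averaged with no effect in the other. The merged class may also be large: at the pilot study's proportions it would hold about two-thirds of patients.

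**Working it through.** **Text comparison.** Question in SAP 9.8: three types. Interaction test in 9.8: two classes. Hazard ratios and Kaplan-Meier rates in 9.8: two classes. Subgroup list in SAP 8.1: most naturally read as two classes. Prespecified subgroup in Protocol 8.1: three types. Baseline comparison in SAP 7.1: three types. The SAP does not avoid three-level subgroups in general, since age has three levels in both 8.1 and 9.8.

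**Is there a plan figure to reproduce?** Not on this point: the documents give no power for any AF-type interaction. The sizes below are illustrations.

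**Inputs**
- AF-type mix 32% paroxysmal, 37% persistent, 32% long-standing persistent, from the 60-patient pilot (Protocol 1.3.2). The main trial's mix is not given, so this is an assumption.
- 338 events, as a scale for the primary endpoint: the Freedman count for HR 0.70, 90% power, two-sided 0.05, which is (1.70/0.30)² × (1.960 + 1.282)² ≈ 338. The Schoenfeld formula gives 331.
- 735 events, as a scale for AF recurrence. SAP 9.8 bases its primary recurrence analysis on CABANA Box patients, about 2/3 of the 2,204 randomized. If half of them recur (an assumption), 0.5 × 2/3 × 2,204 ≈ 735.
- Events split in proportion to the mix, and variance of each log hazard ratio = 4/events. The hazard ratios are assumed.

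**Dilution in the merged class.** Merged HR = exp[(37·ln HR_persistent + 32·ln HR_long-standing)/69].
- Effect only in persistent AF (0.50 and 1.0): exp(37 × (−0.693)/69) = 0.69.
- Effect only in long-standing persistent AF (1.0 and 0.50): exp(32 × (−0.693)/69) = 0.73.
- Effect only in paroxysmal AF: the merged class shows 1.00 and the paroxysmal class keeps its own 0.50.

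**Power of the interaction test.** With w = events/4 in each type, the noncentrality is Σ w(b − b̄)², where b is the log hazard ratio of each class. It is referred to chi-square with 1 df for two classes and 2 df for three. Worked case: effect only in persistent AF, 338 events split 107/124/107. Noncentrality is 2.53 for two classes (power 36%) and 9.42 for three (power 79%).

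| Assumed HR: paroxysmal / persistent / long-standing | 338 events, two vs three classes | 735 events, two vs three classes |
|---|---|---|
| 1.0 / 0.50 / 1.0 | 36% vs 79% | 65% vs 99% |
| 1.0 / 1.0 / 0.50 | 28% vs 76% | 53% vs 98% |
| 0.50 / 1.0 / 1.0 | 84% vs 76% | 99% vs 98% |
| 0.50 / 0.65 / 0.80 | 34% vs 32% | 62% vs 62% |
| 0.50 / 0.75 / 0.75 | 41% vs 32% | 72% vs 62% |

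**Precision for the long-standing type alone.** The 95% CI factor is exp(1.96 × 2/√events). At a 32/101 share of 338 events (107 events) it is ×/÷ 1.46. At an assumed 10% share (34 events) it is ×/÷ 1.96.

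**The case against.** The best defence is that the SAP legitimately fixes levels that the protocol left open. Protocol 8.1 lists the types in a parenthesis and sets no degrees of freedom. Protocol 8.2.1 names three types only for the covariate and says simply type of AF for differential effects. The two-class test is also the better test under some plausible patterns: it wins when only paroxysmal AF differs, and it loses nothing when the effect is graded. These are supplementary or secondary analyses. Those in SAP 8.1 depend on an overall difference being found, their hazard ratios are called descriptive, SAP section 12 promises conservative interpretation, and SAP 8.1 allows further subgroups to be examined.

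Much of this stands. It argues against replacing the two-class test as the lead analysis, and it lowers the stakes. It does not settle the mismatch inside SAP 9.8, where the three-way question is stated outright and then not analysed, and where the analysis does not wait for an overall difference. Permission to look at other subgroups is optional and does not stand in for a prespecified three-type display.

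A reader might infer more than the documents support:
- That every AF-type analysis merges the types. SAP 7.1 keeps three levels, and the coding of the 8.1 covariate is not stated.
- That an effect confined to any one type disappears. A paroxysmal-only effect keeps its own class, and the other two are diluted, not removed.
- That SAP 8.1 certainly specifies two levels. Its punctuation leaves some doubt, although two is the likelier reading.
- That the protocol identifies long-standing persistent AF as the type where ablation benefit is least certain. Protocol 1.1.2 describes progression and mortality, not response to ablation by type.

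**Conclusion.** The point holds for the specified interaction and subgroup analyses. SAP 9.8, followed as written, cannot say whether persistent and long-standing persistent AF respond differently, although it names that comparison as part of a question of key interest. SAP 8.1 most likely has the same limit for the primary endpoint and, by reference, for mortality and the on-treatment subgroups. It departs from the three types in Protocol 8.1 without a stated reason.

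The size depends on assumptions. At the pilot mix, a hazard ratio of 0.50 confined to one of the two merged types would appear as 0.69 to 0.73, and the two-class test would lose roughly 34 to 48 percentage points of power against a three-class test. With a graded effect the loss is about nil, and with a paroxysmal-only effect the two-class test is slightly better. The trial's own mix, event counts and effects by type are not in the documents. The case for change therefore rests on answering the stated question, not on a general gain in power.

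**What to change.** In SAP 9.8 and 8.1, keep the paroxysmal versus non-paroxysmal interaction test and add:
- a hazard ratio with 95% CI for each of the three AF types;
- in 9.8, Kaplan-Meier rates by the three types;
- a supplementary 2-df test of treatment by three-level AF type.

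In SAP 7.1, replace the label permanent with long-standing persistent so that the baseline table uses the categories of Protocol 3.1.

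AF type is an entry criterion and already appears at three levels in the SAP 7.1 baseline comparison, so no new data are needed. The cost is a change of wording, extra rows in the displays and one more supplementary test. If the long-standing persistent group is small its interval will be wide (about ×/÷ 2 at 34 events), and the separate row makes that visible.
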